STATISTICAL METHODS	
This is an exploratory basket study to adequately approach the heterogeneity of clinical conditions included under the concept of immune compromise. The study implements a Bayesian methodology. This decision has been adopted after taking into account the relative low frequency of the conditions under study, the relative absence of prospective data of the outcomes of COVID-19 for the study populations (most of the available data are retrospective and belong to the early waves of the pandemic, with different viral variants than nowadays), along with the changing medical practices in these settings. Under these premises, a Bayesian approach is more appropriate in terms of efficient decision-making process and will

	
provide novel information for future therapeutic development in these clinical conditions.
 
The trial will use a minimally informative prior of $N(0,1)$ to update the information provided by the trial data to produce a posterior distribution.
 
The resultant posterior distribution will serve as a starting point for further trials within this area, whether as a key part of any information data packs provided to experts ahead of an elicitation meeting, or directly as the informed prior or hypotheses for further trials.
 
A calibrated Bayesian hierarchical model (CBHM) described by Chu and Yuan will be used to analyse the data, allowing data to be analysed by group, and results from each group will be used to enrich the data of the other groups. The calibration of the model allows strong information sharing when the treatment effect is similar among baskets and shrinks that sharing towards 0 as the treatment effect becomes more heterogeneous.
 
An overall type I error of 5% will be used to analyse by means of credible regions the OR against a null of $OR=1$ [$\log(OR)=0$], the case where no discernible difference is induced from intervention.
 
Simulation was used to perform sensitivity analysis on a range of informed priors against a minimally informative prior to ensure that its use would not impact the results on the data too far.
 
The statistical methods for this study are described in a detailed statistical analysis plan (SAP).

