	
that a sample size of 40 per basket will allow for a posterior probability around 0.9 in each basket (i.e. 90% probability that the experimental arm is better than the control in each basket), ranging from 0.87 (when the data from the fastest basket is analysed) to 0.915 (at the end of the accrual of the last basket) (type I error rate= 0.05).
 
B) Non-controlled group 4*
 
Many different clinical conditions cannot be classified into one of the 3 randomised groups and have been pooled into a fourth group of 30 patients. As there is a remarkable intragroup heterogeneity, this group will not be controlled and will contribute to the objective of increasing safety knowledge of plitidepsin. A Fleming's Phase II procedure with a 1-stage design has been used to estimate the sample size needed to rule out that plitidepsin induces drug-related SAEs in at least 35% of the patients (null hypothesis), and to confirm that the respective rate is 10 % or lower (alternative hypothesis), with a type I error of 0.05 and a power of 90%.
 
If at least 25 patients out of a total sample of 30 do not experience a drug-related SAE, the null hypothesis will be rejected.
 
*Not applicable in Spain
 
METHODS OF ANALYSIS
 
Analysis of the primary and other time-to-event efficacy endpoints will be performed primarily in the FAS but also in the "Per Protocol" and "As treated" populations. Supportive analyses will be performed on the Per Protocol population. Safety endpoints analyses will be based on the "As treated" Population.
 
Primary endpoint
 
The difference between treatment and control arms in all-cause mortality at 30 days will be examined using a Bayesian comparison of proportions within the calibrated Bayesian hierarchical model (CBHM) framework described by Chu and Yuan. The use of the CBHM allows for flexible information borrowing across all groups, with strong borrowing in the case when treatment effect is homogeneous among the groups and less borrowing as the effect becomes more heterogeneous.
 
In this framework the odds ratio is modelled as $\theta_i = \log(\text{odds}_i)$ with a normal distribution of unknown mean (μ) and variance (σ^2). The prior distribution used by the framework will be a minimally informative prior using $N(0,1)$.
 
The variance (σ^2) represents the degree of heterogeneity between the patient groups, with 0 representing the case where there is homogeneity of

--	---

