	
treatment effect and thus complete pooling of the results across patient groups, with adjustment for targeted p1 rates in each group, whereas a value closer to infinity would lead to no borrowing across groups. These estimates are iteratively updated within the modelling procedure based on the available data.
 
As each basket is completed, they will be evaluated for efficacy, with information gained being used to update the analyses of successive baskets.
 
Once all patients recruited to a basket have completed the trial, a formal analysis will be performed on the patients within the basket. The result will be able to stand on its own for the specific subpopulation, and the information from this analysis will be used to enrich the information at analysis of the proceeding baskets.
 
Results in later baskets will be related to pooled data, however if one basket is not seen to be homogeneous to other baskets, the information from that basket can be run without the pooled information from other baskets and its information not pulled through into later analyses.
 
As a sensitivity analysis the Bayesian hierarchical model will be used.
 
The cut-off for considering further clinical development of plitidepsin in each randomised group will be a posterior probability of superiority for the experimental arm equal to or greater than 65%.
 
Secondary endpoints/Other endpoints
 
Frequency tables will be prepared for categorical variables, and continuous variables will be described by means of summary tables, which will include the median, mean, standard deviation, interquartile range, minimum, and maximum of each variable.
 
In addition to Bayesian methods, frequentist methods will be also calculated. Counts and percentages, with their corresponding exact confidence intervals, will be calculated for the binomial endpoints. Time-to-event variables and their set time estimates will be analysed according to the Kaplan-Meier method and Cox regressions.
 
Safety analyses will include AEs, SAEs, deaths, laboratory evaluations and study drug discontinuations due to AEs will be tabulated in a descriptive way.
 
Pooled and subgroup analyses will be performed, taking into consideration baseline characteristics of the patients and of the underlying disease, risks factors for clinical deterioration or death, vaccination status, duration of the infection prior to study entry, and concomitant therapies (e.g.,

--	--

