8. STATISTICAL METHODS

This is an exploratory basket study to adequately approach the heterogeneity of clinical conditions included under the concept of immune compromise.

The study implements a Bayesian methodology. This decision has been adopted after taking into account the relative low frequency of the conditions under study, the relative absence of prospective data of the outcomes of COVID-19 for the study populations (most of the available data are retrospective and belong to the early waves of the pandemic, with different viral variants than nowadays), along with the changing medical practices in these settings. Under these premises, a Bayesian approach is more appropriate in terms of efficient decision-making process, and will provide novel information for future therapeutic development in these clinical conditions (90).

The trial will use a minimally-informative prior of $N(0,1)$ to update the information provided by the trial data to produce a posterior distribution.

The resultant posterior distribution will serve as a starting point for further trials within this area, whether as a key part of any information data packs provided to experts ahead of an elicitation meeting, or directly as the informed prior or hypotheses for further trials (91) (92).

A calibrated Bayesian hierarchical model (CBHM) described by Chu and Yuan (93) will be used to analyse the data, allowing data to be analysed by group and results from each group will be used to enrich the data of the other groups. The calibration of the model allows strong information sharing when the treatment effect is similar among baskets, and shrinks that sharing towards 0 as the treatment effect becomes more heterogeneous.

An overall type I error of 5% was used in analysing by means of credible regions the OR against a null of OR=1 [$\log(\text{OR})=0$], the case where no discernible difference is induced from intervention.

Simulation was used to perform sensitivity analysis on a range of informed priors against a minimally-informative prior to ensure that its use would not impact the results on the data too far.

The statistical methods for this study are described in a detailed statistical analysis plan (SAP).

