8.1 SAMPLE SIZE CALCULATION

Our intention is to conduct this study with 4 groups of immunocompromised patients.

A) Randomised groups (1-3)

Patients in three of the four groups will be randomly assigned to one of two arms. Each randomised group will have a sample size of 40 patients (20 in the experimental arm, 20 in the control arm).

Given the exploratory nature of this phase II study, this sample size has been chosen based on operational considerations to allow the feasibility of accrual in this relatively small population and also provide preliminary estimates to establish an updated prior distribution of the mortality rates for further investigation using Bayesian methods in a potential Phase III study.

The operating characteristics of the calibrated Bayesian hierarchical model (CBHM) described by Chu and Yuan (93) have been investigated by means of the CBHM package from Yuan at MD Anderson Cancer Center (94), and with reference to the JAGS program running in R version 4.2.1 (95) on Microsoft Windows 10.

Within the CBHM simulations, 5000 Markov-chain Monte Carlo (MCMC) repetitions per scenario were simulated with a range of operating characteristics for the null, alternative and true mortality rates moving from 5% to 95% in steps of 5% ([Table 4](#)). A maximum sample size of 40 per randomised group was set through the CBHM simulations, which in turn determines whether there is a need for the total sample size to be allocated. Within all simulations, the full 120 patients were used, suggesting that this is the minimum sample size that enables decision-making. As an example, if the mortality rate in each group is 20% and we target a clinically meaningful reduction of 12.5% in the experimental arm ($H_0=20\%$, $H_1=7.5\%$), and the assumed true mortality rate is 7.5%, the simulation demonstrates that a sample size of 40 per basket will allow for a posterior probability around 0.9 in each basket (i.e. 90% probability that the

experimental arm is better than the control in each basket), ranging from 0.87 (when the data from the fastest basket is analysed) to 0.915 (at the end of the accrual of the last basket) (type I error rate= 0.05).

Table 4 Example of simulated posterior probabilities for sample size definition.

Mortality rate – control arm (null)	Mortality rate – experimental arm (alternative)	True mortality rate	Sample size per basket	Posterior probability 1st basket	Posterior probability 2nd basket	Posterior probability 3rd basket

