20%	7.5%	7.5%	30	0.82	0.84	0.865
20%	7.5%	7.5%	40	0.87	0.88	0.915
20%	7.5%	7.5%	50	0.895	0.905	0.93
20%	7.5%	7.5%	60	0.905	0.925	0.97
20%	7.5%	7.5%	70	0.945	0.98	0.985
20%	7.5%	7.5%	80	0.96	0.985	0.985

The full output of the simulations performed can be found in the Statistical Analysis Plan.

B) Non-controlled group 4*

Many different clinical conditions cannot be classified into one of the 3 randomised groups and have been pooled into a fourth group of 30 patients. As there is a remarkable intragroup heterogeneity, this group will not be controlled and will contribute to the objective of increasing safety knowledge of plitidepsin. A Fleming's phase II procedure with a 1-stage design has been used to estimate the sample size needed to rule out that plitidepsin induces drug-related SAEs in at least 35% of the patients (null hypothesis), and to confirm that the respective rate is 10 % or lower (alternative hypothesis), with a type I error of 0.05 and a power of 90%.

If at least 25 patients out of a total sample of 30 do not experience a drug-related SAE, the null hypothesis will be rejected.

*Not applicable in Spain

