8.4 ANALYSIS METHODS

8.4.1 Primary Endpoint

The difference between treatment and placebo arms in all-cause mortality at 30 days will be examined using a Bayesian comparison of proportions within the calibrated Bayesian hierarchical model (CBHM) framework described by Chu and Yuan (93). The use of the CBHM allows for flexible information borrowing across all groups, with strong borrowing in the case when treatment effect is homogeneous among the groups and less borrowing as the effect becomes more heterogeneous.

In this framework the odds ratio is modelled as $\theta_i = \log(\text{odds}_i)$ with a normal distribution of unknown mean (μ) and variance (σ^2). The prior distribution used by the framework will be a minimally-informative prior using $N(0, 1)$.

The variance (σ^2) represents the degree of heterogeneity between the patient groups, with 0 representing the case where there is homogeneity of treatment effect and thus complete pooling of the results across patient groups, with adjustment for targeted p1 rates in each group, whereas a value closer to infinity would lead to no borrowing across groups. These estimates are iteratively updated within the modelling procedure based on the available data.

As each basket completes, they will be evaluated for efficacy, with information gained being used to update the analyses of successive baskets.

Once all patients recruited to a basket have completed the trial, a formal analysis will be performed on the patients within the basket. The result will be able to stand on its own for the

specific subpopulation, and the information from this analysis will be used to enrich the information at analysis of the proceeding baskets.

Results in later baskets will be related to pooled data, however if one basket is not seen to be homogeneous to other baskets, the information from that basket can be run without the pooled information from other baskets and its information not pulled through into later analyses.

As a sensitivity analysis the Bayesian hierarchical model will be used.

The cut-off for considering further clinical development of plitidepsin in each randomised group will be a posterior probability of superiority for the experimental arm equal to or greater than 65%.

Sensitivity/supportive analyses for the primary endpoint will be also performed. Frequentist approach for odds ratio comparison: unstratified and stratified considering randomisation and actual strata values.

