6.0 Introduction

This SAP should be read in conjunction with the study protocol and case report form (CRF). Any further changes to the protocol or CRF may necessitate updates to the SAP. A first version of the SAP is expected prior to first patient in (FPI) and final approval of the SAP will occur prior to database lock. Due to low recruitment, early study closure was held on 23Feb24. Therefore, SAP is abridged to provide the essential results for an abbreviated Clinical Study Report (CSR) where information related to safety and descriptive efficacy results will be described. Study objectives, endpoints and populations will be adapted accordingly in order to present the most relevant data.

Consequently, no formal statistical significance tests will be presented, although the descriptive tables will allow a numerical comparison of the characteristics and outcomes of the patients in the experimental and control arm across the subgroups.

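### The 5% type I error printed for Groups 1-3 belongs to no defined rule, and it is not the error rate of the 65% posterior-probability cut-off, the only decision rule those groups have

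*Protocol*

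**What the plan says.** The 5% is printed in two ways.

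- As an overall error for a credible-region analysis. Protocol 8 says: "An overall type I error of 5% was used in analysing by means of credible regions the OR against a null of OR=1". The synopsis (Statistical Methods) has the same statement in the future tense: "An overall type I error of 5% will be used to analyse by means of credible regions the OR". Neither gives a credible level, says whether it is one- or two-sided, defines the scope of overall, or names a decision that follows.
- As a tag on the sample-size simulations. After the example with 40 patients per group, the synopsis, Protocol 8.1 and SAP 8.5 report posterior probabilities running from 0.87 "to 0.915 (at the end of the accrual of the last basket) (type I error rate= 0.05").

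The decision rule is separate. Protocol 8.4.1 says that the cut-off for considering further development "in each randomised group will be a posterior probability of superiority for the experimental arm equal to or greater than 65" per cent. The synopsis and SAP 11.6.1 set the same condition, group by group. No other decision rule is defined for Groups 1-3.

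On supporting evidence, Protocol 8.1 says the simulations covered "operating characteristics for the null, alternative and true mortality rates moving from 5% to 95% in steps of 5" per cent, and adds: "The full output of the simulations performed can be found in the Statistical Analysis Plan". The SAP supplied is version 3.0. Its introduction says the "SAP is abridged to provide the essential results for an abbreviated Clinical Study Report", and its Table 1 has only rows with 20% control, 7.5% alternative and 7.5% true mortality.

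**The concern.** A type I error is a property of a decision rule. Here the figure is printed without a rule, and the rule is printed without an error rate. Someone reading the design section meets 5% in the same sentence as the posterior probabilities, then finds a cut-off on that same quantity, and may join the two. A go in one group would then look like a result controlled at 5% when the criterion is far looser.

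Group 4 shows what a complete statement looks like. Its hypotheses (35% against 10% drug-related SAEs), error, power and rule (at least 25 of 30 patients without such an event) are given together. Groups 1-3 have no such link.

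Little is now at stake in the analysis. What remains is how the abbreviated report describes the design, and any later trial that reuses it. Protocol 8 says the posterior is meant to inform further trials.

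**Working it through.** **Inputs.** 20 patients per arm in each group; example mortality 20% against 7.5% (Protocol 8.1). Go if P(superiority | data) ≥ 0.65 (Protocol 8.4.1). N(0,1) prior (Protocol 8). The prior for the control arm and the calibration of the hierarchical model are not given, so several control priors were tried.

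**Method.** For deaths x_E and x_C out of 20, compute PP(x_E, x_C) = P(p_E < p_C | x_E, x_C). Then, summing over all 21 × 21 outcomes,

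false-go rate = Σ Bin(x_E; 20, p) · Bin(x_C; 20, p) · 1[PP ≥ 0.65], with the same mortality p in both arms.

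The correct-go rate uses 7.5% and 20% instead. There is no borrowing between groups.

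**The plan's own figure first.** Protocol Table 4 gives 0.87 for the first group at 40 patients. The mean posterior at 20% against 7.5% is 0.76-0.80 with vague or Beta priors. A control-logit SD of 1.0 gives 0.868 at 40 per group, but 0.846 at 30 (stated 0.82) and 0.921 at 80 (stated 0.96). No model tried matches the whole column, so what follows shows the size of the gap and is not the sponsor's operating characteristics.

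**The 65% rule at 20% mortality in both arms:**

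| Two-arm model | False-go | Correct-go | Cut-off for false-go ≤ 5% |
|---|---|---|---|
| Beta(1,1) or Beta(0.5,0.5) on each arm | 0.357 | 0.819 | 0.950-0.963 |
| log OR ~ N(0,1), vague control logit (SD 2.5 to 10) | 0.28-0.36 | 0.69-0.82 | 0.908-0.913 |
| same, control-logit SD 1.5 | 0.417 | 0.850 | 0.932 |
| same, control-logit SD 1.0 | 0.486 | 0.916 | 0.943 |

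The range is therefore about 28-49% per group, and a 5% error needs a cut-off of roughly 0.91-0.96. As an example, 3 deaths in 20 on plitidepsin against 4 in 20 on control gives PP = 0.652 under Beta(1,1), which is a go.

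**Other mortality rates.** With the vague and Beta priors, the false-go rate is 0.241-0.390 at 10% mortality and 0.302-0.314 at 30%.

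**With borrowing.** In an illustrative sequential model (mean log OR ~ N(0,1), between-group SD 0, 0.5 or 1.0, control-logit SD 2.5 or 10), the false-go rate per group at 20% is 0.28-0.40. Borrowing of this kind does not bring it near 5%.

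**Single-arm reading.** Protocol 8.4.1 writes the parameter as a log odds, which could be read literally as one arm of 20 against a fixed null rate, with N(0,1) on the logit.

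- Null 20%: a go needs at most 1 death (2 deaths gives PP = 0.648). False-go = 0.8^20 + 20 × 0.2 × 0.8^19 = 0.0115 + 0.0576 = 0.069.
- Null 15%: a go needs 0 deaths. False-go = 0.85^20 = 0.039.
- Null 10% or 5%: no outcome is a go, so false-go = 0.
- With Beta priors at a 20% null: 0.206 for Beta(1,1) and 0.411 for Beta(0.5,0.5).

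This reading can therefore fall below 5%. It fits poorly with the odds-ratio null of 1 in Protocol 8, which is a two-arm comparison.

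**The case against.** The strongest reply is that nothing contradicts anything. The 5% is attached to one comparison and the 65% to another, and an inferential criterion can coexist with a lenient development threshold. SAP 11.6.1 lists a credible interval before it gives the cut-off, and Protocol 8.5 sets the primary analysis apart from exploratory p-values. This stands in part. A reader might infer that the documents claim a 5% error for the 65% rule; no passage does. What does not stand is that the 5% is thereby explained, since the credible-region criterion has no level, sidedness, scope or consequence.

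Three other stronger readings are tempting.

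- *The 65% rule cannot have a 5% error under any model.* The single-arm reading falls below 5% at null rates of 15% or less, which are on the grid Protocol 8.1 says was simulated. The claim is limited to two-arm models.
- *No null scenario was run.* Protocol 8.1 says null and true rates were varied, and SAP 3.0 is openly abridged. An earlier version may hold the output. Its absence here is context, not a separate defect.
- *Table 4 is wrong because it was not reproduced.* Without the control prior and the calibration, that does not follow.

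A lenient cut-off is also legitimate in a study that calls itself exploratory. That is accepted.

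**Conclusion.** The concern holds as a minor reporting defect. A 5% type I error is printed for Groups 1-3 without a rule to which it belongs, and the one rule these groups have is far more lenient: about 28-49% false-go per group at 20% mortality (36% with Beta priors). This rests on a two-arm comparison with 20 per arm, no borrowing and assumed control priors. The exact rate under the sponsor's calibrated model is unknown. It is certain that the 5% is printed and that no decision is tied to it; the size of the gap is only illustrative. No result changes, because SAP 11.6 and 11.6.1 drop the Bayesian outputs after early closure and neither criterion will be applied.

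**What to change.** - In the synopsis, Protocol 8 and 8.1, and SAP 8.5, either remove the 5% or state which credible-region criterion it belongs to: level, one- or two-sided, per group or overall. Add one sentence saying that it is not the error rate of the 65% cut-off.
- If the sponsor's existing simulations or an earlier SAP version hold the false-go and correct-go rates of the 65% rule, cite them where Protocol 8.1 now points to the SAP. New simulation tables are optional. The illustrative ranges above should not be copied in.
- In the abbreviated report, state that neither criterion was applied, and do not present 5% as the error rate of the go decision.

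The 65% cut-off stays as it is. The cost is a few sentences and, where available, one citation; no analysis changes.

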5.6 PATIENT RANDOMISATION

Patients will be sequentially allocated in their respective group, following the algorithm depicted in [Figure 9](#).

Central randomisation will be implemented. In groups 1-3, patients will be assigned to the experimental or the control arms at a 1:1 ratio. Stratification will be performed in the randomised groups. The ISARIC-4C mortality score will be used as a stratification factor in all groups (score <9/≥9). In addition, the type of graft (allogeneic haematopoietic/lung or intestinal/other) will be used for Group 1, whereas the underlying disease will be considered for Groups 2 and 3. For Group 2, the factor categories will be haematological neoplasm vs other disease; the respective categories for Group 3 will be neoplasia vs other. Stratification is not applicable in the non-randomised Group 4.

Day 1 is defined as the day of randomisation. Treatment must start within the same natural day.

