11.8 Summary of Statistical Tests

All the main characteristics for estimands to fulfill study objectives will be defined as footnotes in each table following a similar structure than primary estimand definition. Below it can be found the endpoints to measure the variable definition and the analysis method to be used. Treatment attribute is maintained as 'participants will be randomised to receive plitidepsin versus control in each group' whereas applicable and sensitivity analyses according populations defined in 8.5 will be calculated. For intercurrent events, while applicable, a treatment-policy strategy as defined for the primary estimand will be followed.

Table 3 Summary of statistical tests

Endpoints	Analyses	Population
Efficacy primary endpoint		
1-month all-cause mortality rate.	-Frequencies	-FAS population
Key secondary endpoint		
Time to confirmed negativisation in SARS-CoV-2 antigen test or RT-PCR Ct > 30.	-Kaplan-Meier (unstratified)	-FAS population

Endpoints	Analyses	Population
Efficacy secondary endpoints		
Time to sustained end of COVID-related hospital care from the time of randomisation. Sustained discharge is defined as no subsequent admission within 30 days of initial end of hospital care [up to day 60 (± 3)], related to either COVID-19 or COVID-19 therapy	-Kaplan-Meier (unstratified)	-FAS population
Time to sustained improvement (defined in Protocol Section 7.1.3) and resolution of selected COVID signs/symptoms (See Protocol Appendix 10 - COVID-19 signs/symptoms checklist).	-Kaplan-Meier (unstratified)	-FAS population
Distribution of patients according to their clinical status by the 11-category WHO Clinical Progression Scale, at Days 4 (± 1), 8 (± 1), 15 (± 1), 30 (± 2), and 60 (± 3) (See Protocol Appendix 1 – 11-Point World Health Organization (WHO) Clinical Progression Scale).	-Frequencies	-FAS population
Percentage of patients requiring oxygen therapy on Days 4 (± 1), 8 (± 1), 15 (± 1), 30 (± 2), and 60 (± 3).	-Frequencies	-FAS population
Time to sustained discontinuation (i.e., at least 7 days) of oxygen supplementation.	-Kaplan-Meier (unstratified)	-FAS population
Safety secondary endpoints		
Treatment-emergent adverse events (TEAEs).	-Frequencies (severity grade by NCI-CTCAE v5)	-As treated population
TEAEs \geq grade 3 according to the National Cancer Institute	-Frequencies	-As treated population

Endpoints	Analyses	Population
[NCI]-Common Terminology Criteria for AEs (CTCAE v.5.0).		

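### Randomisation is stratified on ISARIC-4C mortality risk, but the primary mortality model has no ISARIC term and the abridged SAP compares crude deaths by arm without ISARIC strata

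*Protocol*

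**What the plan says.** Protocol 5.6 (repeated in SAP 8.4) states: "The ISARIC-4C mortality score will be used as a stratification factor in all groups". The cut is <9 versus ≥9, and each group has one further factor. In Group 1, "the type of graft (allogeneic haematopoietic/lung or intestinal/other) will be used for Group 1"; Groups 2 and 3 use a two-level disease factor. Within each group "patients will be assigned to the experimental or the control arms at a 1:1 ratio".

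Protocol 8.4.1 makes the primary analysis of 30-day mortality a Bayesian comparison of two proportions within a calibrated hierarchical model. No stratification term is named there or in the estimand in 8.5, and no reason is given. The same section adds a supportive frequentist odds ratio, "unstratified and stratified considering randomisation and actual strata values", and the table in 8.5 lists it again.

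SAP version 3 was abridged after the decision to close early for low recruitment.
- Section 6.0 drops formal tests but says the descriptive tables will let readers compare the arms numerically.
- Section 11.6 removes the hierarchical model and all sensitivity analyses, and combines cohorts for safety only.
- Table 3 in 11.8 gives the primary endpoint as frequencies, and every time-to-event row as "Kaplan-Meier (unstratified".
- Section 11.10 removes subgroup outputs.
- Section 11.2 still summarises the stratification factors at baseline, from both the randomisation form and the clinical forms.
- Table 3 still has a row for mortality or deterioration risk by scores such as ISARIC-4C. Section 7.3 marks the matching objective not applicable, and 8.3 no longer lists the endpoint.

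**The concern.** The common stratification factor is a mortality score and the endpoint is mortality, so ISARIC is the baseline variable most likely to distort a crude comparison of deaths. Stratified randomisation protects against this when cells are well filled. Here the cells are many and small, and accrual stopped early, with SAP 11.6 singling out cohorts 1 and 3 as low. A difference between arms in the share of high-risk patients would pass straight into the crude death rates that readers are invited to compare. The baseline table would show such an imbalance, but not how much of a mortality difference it explains.

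The SAP also leaves unclear whether deaths by ISARIC level will be produced at all, because Table 3 disagrees with 7.3 and 8.3.

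**Working it through.** **1. The plan's own figure.** Protocol 8.1 reasons that "if the mortality rate in each group is 20% and we target a clinically meaningful reduction of 12.5% in the experimental arm", with 20 patients per arm in each group. It reports simulated posterior probabilities of 0.87, 0.88 and 0.915 for the first to third basket. The calibration settings are not given, so these can only be bracketed. Two independent Beta-binomial arms of 20 give a mean posterior of 0.79-0.80. One arm against a fixed 20% gives 0.85-0.91 (n = 20) or 0.94-0.96 (n = 40). The stated values lie within this range and can be neither confirmed nor refuted.

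**2. How thin the cells are.** Stratification cells: Group 1 has 2 × 3 = 6, and Groups 2 and 3 have 2 × 2 = 4 each, so 6 + 4 + 4 = 14 for 120 patients. Expected deaths per group under the design are 20 × 0.20 + 20 × 0.075 = 5.5. With equal cells that is 5.5 / 6 = 0.9 per cell in Group 1 and 5.5 / 4 = 1.4 in Groups 2 and 3. Full stratification is therefore sparse even at full enrolment. ISARIC alone gives two strata per group, or 5.5 / 2 = 2.75 deaths each.

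**3. Effect of an imbalance on crude mortality.** Shift = (difference between arms in the share ≥9) × (mortality ≥9 minus mortality <9). The documents give no mortality by stratum, so these rates are assumed. Take 6 of 10 against 4 of 10 patients at ≥9, a 20-point difference.
- Mortality 10% and 30%: 0.20 × 20 = 4 points, and 4 / 12.5 = 32% of the target effect.
- Mortality 5% and 35%: 0.20 × 30 = 6 points, and 6 / 12.5 = 48%.

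**4. Effect on precision.** Assume half the patients are ≥9, overall mortality p = 20%, and balanced strata.
- Risk difference: the share of outcome variance explained is q(1−q)(p₁−p₀)² / [p(1−p)]. This is 0.25 × 0.04 / 0.16 = 0.0625, or 0.25 × 0.09 / 0.16 = 0.141. The unadjusted standard error is too large by 1/√(1−0.0625) = 1.033, or 1/√(1−0.141) = 1.079.
- Log odds ratio, 20 per arm, no effect: unadjusted SE = √(2/(20 × 0.16)) = 0.791. For 10%/30% the mean within-stratum variance is (0.09 + 0.21)/2 = 0.15, so adjusted SE = √(2/(20 × 0.15)) = 0.816. For 5%/35% it is (0.0475 + 0.2275)/2 = 0.1375, so adjusted SE = √(2/(20 × 0.1375)) = 0.853. Adjustment makes the SE 3.3% or 7.9% larger.

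The ratios are the same on both scales, but the direction reverses.

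**5. Effect on the 65% decision rule.** A logistic model was simulated for one basket of 20 per arm, with an N(0,1) prior on the treatment log odds ratio, balanced strata and no borrowing. One intercept was compared with separate ISARIC intercepts (assumed prior N(−1.5, 3²)). Control mortality in the low/high strata was 20/20, 15/25, 10/30 or 5/35% (half high-risk), or 10/50% (a quarter high-risk).

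| | Unadjusted | ISARIC-adjusted |
|---|---|---|
| P(posterior ≥65%), 20% vs 7.5% | 0.74-0.75 | 0.79-0.81 |
| P(posterior ≥65%), no effect | 0.26-0.29 | 0.29-0.34 |

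The two analyses fell on different sides of 65% in about 3-8% of baskets. Most of the gap is present when ISARIC is not prognostic at all (0.742 against 0.798), so it comes mainly from the priors and sparse data.

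**The case against.** The strongest reply is that the protocol did plan a stratified analysis of the primary endpoint, and that making it supportive is a reasonable choice with about 5.5 expected deaths per group. That stands against any inference that the plan ignores ISARIC altogether.

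A reader might also infer that omitting ISARIC makes the odds-ratio interval too wide. It does not: step 4 shows that adjustment widens that interval slightly, and the 3-8% gain belongs to a risk difference under assumed rates. Nor does step 5 show that the unadjusted model raises the false-go rate; the adjusted one was somewhat higher.

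A third tempting reading is that SAP version 3 discards every stratified output while keeping unstratified inference. In fact it removes the planned treatment-effect tests and models, stratified and unstratified alike. It keeps the baseline tabulation of strata and, ambiguously, an ISARIC mortality row. No treatment-effect interval remains to be too wide.

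The documents give neither enrolment by group nor the block scheme, which SAP 8.4 leaves to a separate randomisation plan, so an actual imbalance cannot be asserted. A Mantel-Haenszel estimate pooled over groups would conflict with the SAP's decision to combine cohorts for safety only. SAP 8.2 dates the decision to unmask to 19 March 2024, so a new primary model for this trial would be a post-unmasking change.

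These replies limit the point. They do not answer it: the SAP invites a comparison of crude deaths by arm and gives no view of it within the risk strata used to randomise.

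**Conclusion.** The concern holds in a limited form. The primary model has no ISARIC term, its absence is not explained, and SAP version 3 keeps no comparison of arms by ISARIC stratum. What is at stake is uncorrected chance imbalance in baseline risk. In the illustration it amounts to 4-6 points of mortality, about a third to a half of the 12.5-point target. This rests on assumed stratum mortality and an assumed 20-point difference in case mix; the true imbalance is unknown and may be nil.

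With balanced strata the model choice matters little: discordant decisions occurred in about 3-8% of simulated baskets, largely for reasons unrelated to ISARIC, in a simplified model without borrowing. Separately, the disagreement between SAP Table 3 and SAP 7.3 and 8.3 is a plain inconsistency that needs resolving.

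**What to change.** **In SAP version 3.** Tabulate 30-day deaths by arm within ISARIC stratum (<9, ≥9) for each randomised group. Optionally add an ISARIC-standardised risk difference within a group where both arms have patients in the strata used, without pooling groups for efficacy. State whether the randomised or the actual stratum is used. Label the table as descriptive and as added after the decision to unmask. Then either keep the ISARIC mortality-risk row in Table 3 and restore the objective and endpoint in 7.3 and 8.3, or delete the row. The cost is one table and a few sentences, since both versions of the strata are already collected.

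**If the Bayesian design is reused.** Include ISARIC as one common covariate with a weakly informative prior, and leave the graft and disease factors to supportive analyses because those cells are too thin. This costs more: the odds ratio becomes conditional on ISARIC, which the estimand must say, and the operating characteristics at the 65% cut-off must be simulated again, because the adjusted model crossed it more often under no effect in the check above. If ISARIC is left out again, give the reason.
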